12.4.5.1 Laboratory Data

All hematology, chemistry, TSH, coagulation, and urinalysis results will be listed by subject for each assessment and descriptive statistics may be tabulated for select criteria. Changes from baseline may be summarized by treatment.

12.4.5.2 Physical Examination

Clinically significant changes in vital signs and clinically significant findings on physical examination will be recorded as AEs. Incidence of subjects with changes from normal physical examination findings at baseline to abnormal during the study may be generated.

12.4.5.3 Twelve-lead ECG

Information on ECGs will be presented in listings. The incidence of subjects with changes from normal ECG findings at baseline to abnormal during the study will be generated as appropriate. Summary of mean/median changes in ECG intervals may be generated on a data-driven basis.

12.4.6 Pharmacokinetic Analysis

The concentration-time data will be used to prepare a population PK model for cobomarsen in subjects. The actual elapsed time from dose will be used in the final PK modeling and parameter calculations. The PK/PD analysis of the study will be used to describe the cobomarsen and its metabolite(s) (if applicable) concentration time profile(s) and exposure/response relationships with respect to PD/clinical/safety endpoints by means of modeling and simulation. Full details of the relevant population PK modeling work (including objectives, relevant endpoints, methodology, software etc.) will be defined in a separate data analysis plan or the study integrated analysis plan. The results of these analyses will be described in a separate report from the clinical study report.

The exact date/time of sample collections (and dosing events) should be recorded (in the eCRF). Although every effort should be made to collect PK blood samples according to the Schedule of Events, blood samples collected outside of the planned window are not to be considered protocol deviations as long as the actual collection date and time is recorded, with the exception of the predose sample, which will be considered a deviation if it is not collected predose.

12.4.7 Planned Interim Analyses

An interim analysis will be performed after approximately 40 subjects are followed for a minimum of approximately 6 months to allow assessment for a 4-month duration of response (ORR4) from the date of initial objective response. A decision to stop the study at interim analysis for superiority will be considered if the one-sided test statistic p-value is < 0.01 (Pocock, et al. 1977). The number of skin ORR4 events required to demonstrate superiority at the interim analysis are shown in [Table 6](#).

Table 6: ORR4 Events Required to Demonstrate Superiority in Skin Objective Response for Interim Analysis ($p < 0.01$)

Vorinostat (N = 18)	Cobomarsen (N = 18)
0/18	6/18
1/18	8/18
2/18	10/18
3/18	11/18
4/18	12/18
5/18	13/18
6/18	14/18
7/18	15/18
8/18	16/18
9/18	17/18
10/18	18/18
11/18	18/18
12/18	18/18

Enrollment will be halted if data from this study or other cobomarsen studies conclusively demonstrate that cobomarsen does not have significant activity in MF.

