The analysis of the primary efficacy endpoint is the proportion of subjects in the randomized period achieving an ORR4 in skin by mSWAT assessments. The statistical test for the primary efficacy endpoint will be one-sided and will be split between the interim and final analysis and conducted using a total 0.025 significance level. Additional details of the primary efficacy endpoint in addition to the secondary efficacy endpoints will be detailed in the statistical analysis plan.

	
Safety analyses will include AEs, concomitant medications, laboratory data, physical examination, and ECG data.
 
The following analysis populations will be defined:
 
Intent to Treat Analysis Set (ITT)
 
The ITT will include all randomized subjects who received at least one dose of study treatment (cobomarsen or vorinostat) and had at least one post-baseline assessment.
 
Safety Set
 
The Safety set will include all randomized subjects who received at least one dose of study treatment (cobomarsen or vorinostat).
 
Per Protocol Set (PPS)
 
The PPS will consist of all subjects randomized to the study, who received study treatment, and completed assessments necessary for the evaluation of the primary endpoint with no major protocol deviations that would affect endpoint analysis.
 
Pharmacokinetic Analysis Set (PKAS)
 
The PKAS will consist of subjects randomized to cobomarsen who received at least one dose of cobomarsen and had at least one post baseline PK sample taken and analyzed.

Sample Size Justification:
	
Total enrollment of approximately 126 subjects randomized 1:1 provides greater than 80% power to detect a 25% difference (35% vs 10%) in the primary outcome, ORR₄, between the investigational product and active comparator groups.

Planned Interim Analysis:
	
An interim analysis will be performed after approximately 40 subjects are followed for a minimum of approximately 6 months.

Trial-specific Committees:
	
Data Monitoring Committee
 
The Data Monitoring Committee (DMC) will be responsible for reviewing safety data at regular intervals as well as to perform the interim analysis for futility. A separate DMC Charter will be established that outlines DMC membership, precisely what data will be reviewed, along with the timing and frequency of the reviews. DMC recommendation will be provided to the Sponsor in compliance with the DMC Charter.

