4.1 Randomized Period

Approximately 126 subjects are expected to be enrolled. An interim analysis will be conducted after approximately 40 subjects have been followed for a minimum of approximately 6 months; enrollment will be suspended after approximately 40 subjects have been enrolled until the completion of the interim analysis.

Subjects will be randomized in a 1:1 ratio to receive cobomarsen or vorinostat. Subjects will undergo Screening lasting up to 28 days from the time of informed consent, followed by active treatment, and then follow-up for response and disease progression.

Figure 1. SOLAR Study Design Schematic

Subjects will remain on their assigned study treatment until one of the following occurs:

1. Disease progression, defined as either (see [Appendix F](#)):
 - a. Confirmed progression in skin
 - b. Clinical progression in other compartments, documented by assessments (flow cytometry and/or CT scan) completed per investigator discretion
 - c. Partial or complete skin response followed by a confirmed loss of skin response as defined by an increase of mSWAT of greater than the sum of nadir plus 50% baseline score.

Progressions based on mSWAT will be confirmed by repeated measurement 28 days (± 3 days) after the first determination of progression.

If confirmed, the date of progression will be based on the first determination of progression. Subjects will continue the study treatment until disease progression is confirmed.

2. Subject meets one of the other treatment discontinuation criteria (see [Section 5.4.1](#)).

Safety assessments will include monitoring the incidence and severity of AEs and SAEs, physical examination findings, vital signs, ECG monitoring, and clinical laboratory assessments.

Samples will be collected for PK in the cobomarsen group on Days 1, 2, 3, 5, 8, 15, 29, and every 4 weeks from Weeks 9 through 81, every 8 weeks thereafter, and at the follow-up/end of treatment visit.

mSWAT evaluations will be completed on Days 1 and 29, every 4 weeks through Week 81, every 8 weeks thereafter, and at the End of Treatment and Follow-up visits. Every effort will be made to perform a final disease assessment for subjects who withdraw from the study early.

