12.2 Study Hypotheses

The primary endpoint is objective response in skin of at least 4 months duration (ORR4).

Response to cobomarsen will be compared to the control group using a Cochran-Mantel-Haenzel (CMH) statistic incorporating the stratification factors from the randomization.

The randomization will be stratified based on subjects with at least one skin tumor at Screening vs. no skin tumors at Screening. Subjects will also be stratified based on prognostic factors (age at diagnosis > 60 years and LDH level > ULN at diagnosis) (Scarlsbrick et al. 2015). Subjects will be stratified based on having 0-1 vs 2 of these prognostic factors.

There is only one primary and one key secondary endpoint (PFS) for analysis; a one-sided $p=0.025$ for response by CMH will establish statistical significance. The study hypothesis is that response to cobomarsen is superior to the control group. The null hypothesis (H_0) is that N (%) of responders to cobomarsen and N (%) of responders to control do not differ; the alternative hypothesis (H_a) is that N (%) of responders to cobomarsen is superior to N (%) of responders to control. A step-down procedure will be used to assess the statistical significance of PFS, such that a statistically significant difference in PFS will be confirmatory of a treatment effect only if the analysis of the primary endpoint is statistically significant at the one-sided 0.025 level of significance.

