12.5 Sample Size Determination

12.5.1 Primary Endpoint Sample Size

A sample size of 126 subjects (63 per group) provides greater than 80% power to detect a difference between cobomarsen and vorinostat, after accounting for the alpha spend at the interim analysis (interim alpha = 1%, one sided). This power statement assumes a response rate of 35% in the cobomarsen group and 10% in the vorinostat group, using a one-sided, two sample binomial test of proportions at the adjusted final one-sided alpha of 1.5% (total alpha = 2.5%, one sided). The planned primary analysis will account for all randomized subjects. Power was computed using the normal approximation method. When the normal approximation method is used to compute power for Fisher's Exact Test, the results are based on the pooled, continuity-corrected Chi-Square test (i.e. Z-Test C.C. (Pooled)). ([Kim et al. 2017](#)).

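### Interim superiority (12.4.7): the p<0.01 rule names no test, and Table 6's required counts follow Fisher's exact test while 12.2 names a stratified CMH, so the two can give opposite signals

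*Combined protocol and SAP*

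**What the plan says.** Section 12.4.7 places the interim after approximately 40 subjects have about 6 months of follow-up. Stopping for "superiority will be considered if the one-sided test statistic p-value is < 0.01"; the sentence does not say which test produces that p-value. The section then states: "The number of skin ORR4 events required to demonstrate superiority at the interim analysis are shown in" Table 6. The table's columns are headed 18 per arm ("Vorinostat (N = 18"), and it lists a minimum cobomarsen count for each of 0 to 12 vorinostat responders.

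Four other places bear on this:

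- Section 12.2 compares ORR4 between arms "using a Cochran-Mantel-Haenzel (CMH) statistic incorporating the stratification factors from the randomization". It does not limit that to the final analysis.
- The synopsis (Statistical Methods) says: "The statistical test for the primary efficacy endpoint will be one-sided and will be split between the interim and final analysis". It names no test.
- Section 12.5.1 computes power "using a one-sided, two sample binomial test of proportions at the adjusted final one-sided alpha of 1.5" per cent, and mentions Fisher's exact test only when describing the power approximation. It adds: "The planned primary analysis will account for all randomized subjects".
- Section 4.1 says "enrollment will be suspended after approximately 40 subjects have been enrolled until the completion of the interim analysis", with 1:1 allocation.

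**The concern.** The stopping criterion is given twice, once as a p-value and once as counts described as required. The two agree only if the p-value comes from one particular test at one particular pair of arm sizes, and the plan states neither condition. If the interim uses the test that 12.2 names, a borderline result can satisfy p<0.01 and miss the table, or occasionally the reverse. Nothing says which prevails.

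The data monitoring committee would then have to settle the threshold after seeing the data, in an open-label trial. If the CMH is intended but the table is followed, the interim also loses power.

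**Working it through.** **Inputs.** From 12.4.7: the one-sided 0.01 threshold, Table 6 and its 18 per arm. From 12.5.1: response rates of 35% and 10%. From 4.1: 1:1 allocation and a pause at about 40, so roughly 20 per arm.

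**Formulas.** Let a and b be cobomarsen and vorinostat responders, n1 and n2 the arm sizes, N = n1 + n2 and m = a + b.

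- Fisher, one-sided: p = sum over x ≥ a of C(n1,x)·C(n2,m−x)/C(N,m).
- CMH, single stratum: z = (a − n1·m/N)/√V, with V = n1·n2·m·(N−m)/(N²(N−1)); p is the upper normal tail.

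**Step 1: reproduce Table 6.** Smallest cobomarsen count with p<0.01 at 18 v 18, for 0 to 12 vorinostat responders:

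| Rule | 0 | 1 | 2 | 3 | 4 | 5 | 6 | 7 | 8 | 9 | 10 | 11 | 12 |
|---|---|---|---|---|---|---|---|---|---|---|---|---|---|
| Table 6 | 6 | 8 | 10 | 11 | 12 | 13 | 14 | 15 | 16 | 17 | 18 | 18 | 18 |
| Fisher | 6 | 8 | 10 | 11 | 12 | 13 | 14 | 15 | 16 | 17 | 17 | 18 | 18 |
| CMH, unstratified | 5 | 7 | 9 | 10 | 11 | 13 | 14 | 14 | 15 | 16 | 17 | 17 | 18 |

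Fisher matches 12 of 13 rows and the unstratified CMH matches 3. Pooled and unpooled z, continuity-corrected z, Boschloo and Barnard tests do not reproduce the table either. That Table 6 is a Fisher table is therefore an inference, but a strong one.

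The exception is the row for 10 vorinostat responders. There 17/18 suffices: (18·43,758 + 48,620)/94,143,280 = 0.0089, the same p as the table's own 8/18 v 1/18. The printed 18/18 gives p=0.0014, so the slip is conservative. At a 10% vorinostat rate, 10 of 18 has probability 1.9 in a million.

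**Step 2: where the rules disagree at 18 per arm.**

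- 9/18 v 2/18 misses Table 6, which asks for 10. Fisher p = 0.0137. CMH: expected 11/2 = 5.5; V = 18·18·11·25/(36²·35) = 1.964; z = 3.5/1.401 = 2.50; p = 0.0063.
- 5/18 v 0/18 misses Table 6, which asks for 6. Fisher p = 8,568/376,992 = 0.0227. CMH: V = 18·18·5·31/(36²·35) = 1.107; z = 2.5/1.052 = 2.38; p = 0.0088.

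**Step 3: how often this matters.** Full binomial enumeration at 35% v 10%, 18 per arm: Table 6 is crossed in 19.9% of trials and unstratified CMH in 30.8%, a gap of 10.9 points.

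**Step 4: stratification.** The plan gives no stratum sizes, so the layouts here are assumed. For 9/18 v 2/18, enumerating every placement of responders gives a largest stratified p of 0.0083 in four layouts with arms balanced within strata. With unbalanced strata it can exceed 0.01: 0.0110, 0.0159 and 0.0204 in three layouts. In the last of these (cobomarsen 9/5/3/1, vorinostat 7/3/5/3), 8/18 v 1/18 meets Table 6 but can have stratified p=0.0125. The same totals can fall either side of 0.01.

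Simulated crossing for the stratified test at 35% v 10%, with equal rates across strata, was 27.7% to 31.0% in balanced layouts and 25.0% to 27.6% with unrestricted imbalance.

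**Step 5: arm sizes, if Fisher is intended.**

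- 20 v 20: 6 v 0 just misses, 38,760/3,838,380 = 0.0101. The rows for 1, 2 and 3 vorinostat responders are unchanged. Printed counts used unchanged are crossed in 24.6% of trials at 35% v 10%, of which 2.2 points have Fisher p ≥ 0.01.
- 19 cobomarsen v 17 vorinostat: the first three rows miss, with p = 0.0139, 0.0146 and 0.0111.
- 17 cobomarsen v 19 vorinostat: every printed count that can be reached (0 to 9 vorinostat responders) still gives p<0.01.

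**Step 6: type I error.** Table 6 at 18 per arm: 0.10% at a 10% null rate, maximum 0.57%. Its counts used at 20 per arm: 0.15% and a maximum of 1.05%.

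**The case against.** The strongest reply is that this is a clarity gap. The criterion is p<0.01; 12.2 already names the ORR4 test without restricting it to the final analysis; Table 6 prints its own N; and crossing means only that stopping will be considered. The protocol defers statistical detail to a SAP and interim conduct to a DMC charter. Neither was available here, and either may name the test. The Fisher and CMH criticisms are also alternatives: if Fisher governs, the CMH mismatch disappears, and if CMH governs, checking rows against Fisher is beside the point.

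Much of that stands, and it rules out several stronger readings a reader might infer:

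- *Table 6 holds only at exactly 18 v 18.* Too strong. At 19 cobomarsen v 20 vorinostat, Fisher minima match 11 of 13 rows. At 19 v 21 every printed count gives p<0.01. At 20 v 20, among the rows for 0 to 3 vorinostat responders, only the zero row fails; those four rows make up 99.2% of Table 6 crossings at that size under 35% v 10%.
- *36 contradicts approximately 40.* The number is approximate, and the ITT set requires a dose and a post-baseline assessment, so fewer than 40 analysed is foreseeable. The gap is unexplained, not contradictory.
- *The 10/18 row is a material error.* It is conservative and almost unreachable.
- *Table 6 is always the stricter rule.* Mostly, but not under every stratified layout.

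What the reply does not remove is that the counts are described as required and do not match the only analysis test the protocol names for this endpoint.

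**Conclusion.** The point holds in this limited form: 12.4.7 states a threshold and a table that can give opposite stopping signals, and it does not say which governs. The firm part is the mismatch between Fisher-type counts and the CMH of 12.2, worth 10.9 points of interim crossing probability at 35% v 10% and 18 per arm when the CMH is unstratified. The stratified figures depend on assumed layouts and show what can happen, not what is likely.

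Two inferences support it: that Table 6 was built with Fisher's test (12 of 13 rows), and that the CMH applies at the interim (12.2 read with the synopsis). Dependence on arm size and the 10/18 row are secondary.

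A reader might infer that the interim threatens overall error control. The figures do not support that: Table 6 stays well below 1% at 18 per arm, and its counts reach only 1.05% at worst at 20 per arm. The cost is an unclear threshold and, if the CMH is meant, lost interim power. Severity is minor to should-fix.

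**What to change.** Before the interim, amend 12.4.7 to:

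1. Name the interim test: the stratified CMH, to match 12.2, unless the sponsor states Fisher instead.
2. State that the p-value from that test, on the subjects in the interim cut, governs.
3. Relabel Table 6 as illustrative, with its test and N stated.

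If a Fisher table at 18 per arm is kept, correct the 10/18 row to 17/18. At 20 per arm the Fisher minima for 0 to 12 vorinostat responders are 7, 8, 10, 11, 13, 14, 15, 16, 17, 17, 18, 19, 19.

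The edit is one or two sentences and a table. The choice of test has a price either way. Fisher at 20 per arm keeps type I error at or below 0.47% but crosses in only 22.4% of trials at 35% v 10%. The CMH crosses more often (35.8% unstratified at 20 per arm), but as an asymptotic test it can slightly exceed 1%: the unstratified maximum is about 1.08% at 18 per arm and 1.13% at 20. Any unstratified CMH table should carry a note that the stratified p-value can differ from it.

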12.5 Sample Size Determination

12.5.1 Primary Endpoint Sample Size

A sample size of 126 subjects (63 per group) provides greater than 80% power to detect a difference between cobomarsen and vorinostat, after accounting for the alpha spend at the interim analysis (interim alpha = 1%, one sided). This power statement assumes a response rate of 35% in the cobomarsen group and 10% in the vorinostat group, using a one-sided, two sample binomial test of proportions at the adjusted final one-sided alpha of 1.5% (total alpha = 2.5%, one sided). The planned primary analysis will account for all randomized subjects. Power was computed using the normal approximation method. When the normal approximation method is used to compute power for Fisher's Exact Test, the results are based on the pooled, continuity-corrected Chi-Square test (i.e. Z-Test C.C. (Pooled)). ([Kim et al. 2017](#)).

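### Adding 1% and 1.5% leaves about 0.2 points of the one-sided 2.5% for ORR4 unspent; a final level near 1.73% would use it, and Section 12.2 must carry the same level

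*Combined protocol and SAP*

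**What the plan says.** - **Section 12.5.1** computes power at 63 per group "after accounting for the alpha spend at the interim analysis (interim alpha = 1%, one sided"), with the final test "at the adjusted final one-sided alpha of 1.5% (total alpha = 2.5%, one sided"). It assumes ORR4 rates of 35% and 10%, uses the pooled, continuity-corrected normal approximation, and claims power above 80%.
- **Synopsis, Statistical Methods** says the one-sided primary test "will be split between the interim and final analysis and conducted using a total 0.025 significance level".
- **Section 12.4.7** sets the timing: "An interim analysis will be performed after approximately 40 subjects are followed for a minimum of approximately 6 months". It gives the rule: "A decision to stop the study at interim analysis for superiority will be considered if the one-sided test statistic p-value is < 0.01", citing Pocock's 1977 paper. Table 6 lists the event counts needed with 18 subjects per arm ("Vorinostat (N = 18") for each drug.
- **Section 12.2** puts significance for the primary CMH test at one-sided 0.025. It lets PFS count as confirmatory only if the primary is significant at that same 0.025. It does not mention the interim look or the 1.5%.

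**The concern.** The final 1.5% is what remains after subtracting 1% from 2.5%. Subtraction treats the two chances of a false positive as if they never overlapped. They do overlap, because the first 40 or so subjects contribute to both analyses, so a trial that crosses at the interim is also more likely to cross at the end. Counting the overlap twice makes the final test stricter than a 2.5% total requires.

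ORR4 is the only primary endpoint and it gates PFS, so power lost on ORR4 is also lost on the one key secondary endpoint. There is a second issue in the opposite direction. A reader who follows Section 12.2 would test at 0.025 at the end, which overspends once a 1% look has been taken. The final level should be stated once and used in every place.

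**Working it through.** **Inputs.** Interim level 0.01, final level 0.015, total 0.025, 63 per arm, rates 0.35 and 0.10 (Section 12.5.1). Interim of about 40 subjects, or 36 in Table 6 (Section 12.4.7). Final level 0.025 in Section 12.2.

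**1. The plan's own figures.** The levels add up: 0.010 + 0.015 = 0.025.

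Power by the pooled, continuity-corrected formula is Φ[(d − 1/n − z·SE0)/SE1], where:
- d = 0.35 − 0.10 = 0.25 and n = 63, so 1/n = 0.0159
- mean rate = 0.225, so SE0 = √(2 × 0.225 × 0.775/63) = 0.0744
- SE1 = √((0.35 × 0.65 + 0.10 × 0.90)/63) = 0.0710
- z at 0.015 = 2.170

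This gives Φ(1.024) = 84.7%, so the claim of more than 80% holds. The same formula needs 58 per arm for 80%.

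**2. Actual overall error.** With equal allocation, the correlation between the two statistics is the square root of the interim fraction. Under the null,

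P(either look crosses) = a1 + a2 − P(both cross), from the bivariate normal.

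| Interim | Correlation | P(both cross) | Overall error at 1% and 1.5% |
|---|---|---|---|
| 40/126 | √0.317 = 0.563 | 0.0021 | 0.0229 |
| 36/126 | √0.286 = 0.535 | 0.0019 | 0.0231 |

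**3. Final level that spends exactly 2.5%.** Solve 0.01 + c − P(both cross) = 0.025 for c.

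| Interim | c | z | Power, 63 per arm |
|---|---|---|---|
| 40/126 | 0.0173 | 2.112 | 86.1% |
| 36/126 | 0.0171 | 2.118 | 86.0% |

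**4. Worth in subjects.** At the 1.5% level, 65 per arm give 86.0%. At the 1.73% level, 61 per arm give 84.7%. For 80% power the requirement falls from 58 to 56 per arm. All three comparisons put the gain at about two subjects per arm.

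**5. Other ways of computing power.** Without the continuity correction, power goes from 89.4% to 90.5%. By exact enumeration of Fisher's test it goes from 86.7% to 88.1%. Counting success at either look, with the correction, it goes from 85.0% to 86.4%.

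**6. Section 12.2 taken literally.** With 0.01 at the interim and 0.025 at the end, the overall error at 40/126 is 0.01 + 0.025 − 0.0029 = 0.0321. At 36/126 it is 0.0323.

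**The case against.** The strongest reply is that nothing here is wrong. An additive split is valid whatever the dependence between looks, it holds type I error at or below 2.5%, and the power target is already met. That stands, and the point is therefore an efficiency gain only.

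Some stronger readings are tempting but not supported:

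- **That the plan assumes the looks are independent.** A Bonferroni sum assumes nothing about dependence. Independence would give a final level of 1 − 0.975/0.99 = 1.515%.
- **That the levels contradict the Pocock citation.** Pocock's equal levels would be about 1.38% each at 40/126, so 1% and 1.5% are not that design. But Section 12.4.7 attaches the reference to the interim rule and nowhere promises equal levels. At most the citation needs clarifying.
- **That a final level near 2.1% is available because Table 6 is so strict.** The first four rows of Table 6 are the smallest counts that give a one-sided Fisher p below 0.01. The true size of such a rule at 18 per arm is well under 1%: 0.0010 at a common rate of 10% and 0.0057 at 50%. The unspent amount therefore depends on an unknown null rate, and 2.1% should not be used.

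It can also be said that the documents leave analysis detail to a later SAP. That is a reason to put the level there, but Sections 12.2 and 12.5.1 already give different final levels and need reconciling in any case.

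**Conclusion.** The point holds as a free improvement of modest size. About 0.2 points of the one-sided 2.5% are unspent (2.29% used at 40/126, 2.31% at 36/126). Spending them moves the final level from 1.5% to about 1.73%, adding about 1.4 points of power on the plan's own formula. A reader might infer that the trial is underpowered or that its error control fails under Section 12.5.1; neither is so.

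The figures rest on the normal approximation, on the interim spending its full 1%, and on an interim at 40 (or 36) of 126. Discrete tests will spend somewhat less. The level must be recomputed at the fraction actually reached.

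The disagreement between Sections 12.2 and 12.5.1 has the larger error consequence. If 0.025 were applied at the final look after a 1% interim, overall error would be about 3.2%. Changing Section 12.5.1 alone would leave that conflict in place.

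**What to change.** Replace the fixed 1.5% in Section 12.5.1 with:

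> The final one-sided level is the value c for which P(interim p < 0.01 or final p < c) = 0.025 under the null, from the bivariate normal joint distribution of the two test statistics at the actual interim fraction (0.0173 at 40/126, 0.0171 at 36/126).

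Fix this rule before any interim data are seen. It remains valid if the trial continues after crossing at the interim, which matters because stopping is only to be considered.

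Give the same final level in the Synopsis (Statistical Methods) and in Section 12.2, both for the primary test and for the condition that opens PFS, so that 0.025 is clearly the total over both looks. Update the power statement in Section 12.5.1 to match.

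The cost is one rule, one calculation once the interim fraction is known, and matching edits in three places. No subjects are added and overall type I error stays at 2.5%.
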